## ABBREVIATIONS

AE	–	Adverse Event
CFR	–	Code of Federal Regulations
CPT	–	Consumer Product Testing Company, Inc.
CRF	–	Case Report Forms
CTCAE	–	Common Terminology Criteria for Adverse Events
GCP	–	Good Clinical Practice
HIPAA	–	Health Insurance Portability and Accountability Act
ICF	–	Informed Consent Form
IRB	–	Institutional Review Board
ISO	–	International Organization for Standardization
ITA°	–	Individual Typology Angle
MED	–	Minimal Erythematol Dose
MEDu	–	Minimal Erythematol Dose on unprotected skin
MEDp	–	Minimal Erythematol Dose on protected skin
PI	–	Principal Investigator or designee
SAE	–	Serious Adverse Event
SOP	–	Standard Operating Procedure
SPF	–	Sun Protection Factor
SPFi	–	Individual Sun Protection Factor
UV	–	Ultraviolet
UVA	–	Ultraviolet A
UVB	–	Ultraviolet B
UVR	–	Ultraviolet Radiation

## DEFINITIONS

**Adverse Event (AE):** Any untoward medical occurrence in a clinical trial subject, temporally associated with the use of a trial product, including any washout or lead-in product (or medical device), whether or not considered related to the trial product, including any washout or lead-in product (or medical device).

**Approximately:** A variance of 10% in the stated value is acceptable.

**Belmont Report:** A document entitled "Ethical Principles and Guidelines for the Protection of Human Subjects of Research" that was produced by the National Commission for the Protection of Human Subjects of Biomedical and Behavioral Research in 1978. The Belmont Report identifies three fundamental ethical principles for all human subjects' research: respect for persons, beneficence, and justice.

**Blinding:** When research participants are unaware of the assigned "treatment." In a single-blinded trial, the subjects do not know what treatment they are receiving. In a double-blinded trial, the subjects AND the investigators are unaware of the treatment assigned, as are the monitors and statisticians in some cases. The objective of blinding is to limit the occurrence of conscious and unconscious bias in the conduct of and interpretation of a clinical trial. Such bias could arise from the influence that knowledge of treatment may have on the recruitment and allocation of subjects, subjects' subsequent care, the attitudes of subjects to the treatments, the assessment of endpoints, the handling of withdrawals, the exclusion of data from analysis, and so on. The essential aim of blinding is to prevent identification of the treatments until all such opportunities for bias have been minimized.

**Case Report Form (CRF):** A record of information collected on each subject during the clinical trial. CRFs are also source documents.

**Clinical Investigation:** A systematic trial designed to evaluate a test material in humans.

**Clinical Research:** A trial in human subjects.

**Clinical Trial:** Any research study that prospectively assigns human participants or groups of humans to one or more interventions to evaluate the effects on outcomes. The terms "research", "clinical research", "clinical study", "study", "clinical trial", "trial", and "clinical investigation" are deemed synonymous.

**Control Standard:** For reference purposes, a control standard is run concurrently with the test material during the testing procedure (aka, "reference sunscreen formulation").

**Declaration of Helsinki:** A series of guidelines adopted by the 18th World Medical Assembly in Helsinki, Finland in 1964 and amended subsequently. Recommendations include the procedures required to ensure subject safety in clinical trials, including informed consent and Ethics Committee reviews.

**Erythema:** Reddening of the skin caused by UVR.

**Ethics Committee:** An independent group of medical and nonmedical people who verify the integrity of a trial and ensure the safety, integrity, and human rights of the subjects (see Institutional Review Board).

**Exclusion Criteria:** Characteristics that would prevent a subject from qualifying for a research trial, as specified in the protocol.

**Full Spectrum UV Radiation:** UV radiation that includes both UVB (290 nm – 320 nm) and UVA (320 nm – 400 nm).

**Good Clinical Practices (GCPs):** International ethical and scientific quality standards for the design, conduct, monitoring, recording, auditing, analysis, and reporting of trials.

**Health Insurance Portability and Accountability Act (HIPAA):** Legislation passed in 1996 that includes a privacy rule creating national standards to protect personal health information.

### CONFIDENTIAL

This document is a confidential communication of Consumer Product Testing Company, Inc. containing Testing Facility capabilities and processes, and as such, is intended solely for the use of the Sponsor and Testing Facility in the performance of services. The confidential information contained herein, shall only be released by either Party upon compelled disclosure in compliance with legal or regulatory requirement.

**Inclusion Criteria:** A list of requirements that a subject must meet to qualify for a research trial, as specified in the protocol.

**Individual Sun Protection Factor (SPFi):** Ratio of the minimal erythema dose on test material protected skin (MEDp) to the minimal erythema dose on unprotected skin (MEDu) of the same subject:

$$\text{SPFi} = \frac{\text{MED (protected skin)}}{\text{MED (unprotected skin)}} = \frac{\text{MEDp}}{\text{MEDu}}$$

**Individual Typology Angle (ITA°):** A value characterizing the skin color of the subject.

**Informed Consent:** The verification of a person's willingness to volunteer in a research trial. The verification is requested only after the person has received complete, objective information about the research, including its objectives, potential benefits, risks and inconveniences, alternative therapies that may be available (if applicable), and the subject's rights and responsibilities in accordance with the current revision of the Declaration of Helsinki (as amended). Consent is given by executing the Informed Consent Form (ICF).

**Institutional Review Board (IRB):** Any board, committee, or other group formally designated by an institution to review, approve the initiation of, and to conduct periodic review of research involving human subjects in compliance with 21 CFR 56. The primary purpose of such review is to assure the protection of the rights and welfare of the human subjects. The term has the same meaning as the phrase institutional review committee as used in section 520(g) of the act.

**Investigator:** A medical professional, usually a physician but also sometimes a nurse, pharmacist, or other professional, under whose direction a test material is given or dispensed. A principal investigator (PI) is responsible for the overall conduct of the clinical trial.

**MedWatch Program:** A national educational/promotional initiative to educate health professionals about the importance of reporting serious adverse events and important product problems, to facilitate reporting to the FDA if they choose to do so, and to provide feedback to the health professional community as new safety information becomes available.

**Minimal Erythema Dose (MED):** The lowest dose of ultraviolet radiation (UVR) that produces the first perceptible unambiguous erythema with defined borders appearing over most of the field of UV exposure, 16 h to 24 h after UV exposure.

**Monitor:** Sponsor or CRO representative who reviews trial records to determine that it is being conducted according to the protocol.

**Monitoring:** Reviewing a clinical trial, ensuring that conduct, proper records, and reports are in accordance with the approved protocol, standard operating procedures, GCPs, and regulatory requirements.

**Panel:** A group of subjects with a unique combination of test materials applied and a unique trial schedule.

**Protocol:** A detailed plan that sets forth the objectives, design, and methods for a clinical trial.

**Protocol Amendment:** Changes or clarifications made in writing to the original protocol.

**Qualified Subject:** A subject who has executed an Informed Consent Form and met all inclusion and exclusion criteria for the clinical trial.

**Quality Assurance:** Systems and procedures designed to ensure that a trial is being performed in compliance with the approved protocol, standard operating procedures, GCPs, and that the data being generated are accurate.

**CONFIDENTIAL**

This document is a confidential communication of Consumer Product Testing Company, Inc. containing Testing Facility capabilities and processes, and as such, is intended solely for the use of the Sponsor and Testing Facility in the performance of services. The confidential information contained herein, shall only be released by either Party upon compelled disclosure in compliance with legal or regulatory requirement.

**Randomization:** A method of assigning trial test material such that each subject has an equal chance of being assigned to each treatment or control group. Randomization guards against selection bias.

**Serious Adverse Event (SAE):** Any adverse event (AE) that is fatal, life-threatening, or permanently disabling, or that results in new or prolonged hospitalization, in a congenital anomaly/birth defect, or is an important medical event.

**Source Data:** All information contained in original records and certified copies of results or observations.

**Source Document:** A document or form that is used to capture original, trial-related data or information. A source document may serve as the Case Report Form or the information may be transcribed onto a Case Report Form.

**Sponsor:** Individual, company, institution, or organization that takes responsibility for initiation, management, and financing of research.

**Standard Operating Procedures (SOPs):** Official, detailed, written instructions for the management of clinical trials. SOPs ensure that all the functions and activities of a clinical trial are carried out consistently and efficiently.

**Subject:** A patient or healthy person participating in a research trial.

**Sun Protection Factor (SPF):** The arithmetic mean of all valid individual SPFi values obtained from all subjects in the test.

**Test Area:** The area of the back between the scapula line and the waist.

**Test Material:** Any material or product that is the subject of testing or a clinical trial. This may also be referred to as a "test article" or "investigational material".

**Test Site:** The site where a test material or control standard is applied or the site used for the determination of the unprotected MED.

**Test Subsite:** An area within the test site that is exposed to UVR.

**Ultraviolet Radiation (UVR):** The radiation from 290 nm to 400 nm, with that from 290 nm to 320 nm being termed UVB, that from 320 nm to 340 nm being termed UVAII and that from 340 nm to 400 nm being termed UVAI.

## 1 Background Information

A sunscreen product in a form suitable for topical administration is generally recognized as safe and effective if it meets the requirements in the International Standard Test Method ISO24444 (2010) (reference 12.1). This protocol is designed to evaluate the Sun Protection Factor (SPF) of the test materials as sunscreen products, as per the requirements delineated in this methodology. In addition, this static methodology meets the requirements of the Australia/New Zealand standard (reference 12.2).

## 2 Trial Objective

The primary objective of this trial is to determine the SPF of two test materials using the methodology described in the International Standard Test Method (reference 12.1). This static methodology also meets the requirements of the Australia/New Zealand standard (reference 12.2).

## 3 Proposed Schedule

Proposed trial initiation, completion, and estimated reporting dates will be established prior to the start of testing.

## 4 Test Materials

### 4.1 Identification

ChapStick Moisturizer, Classic Flavor (CCI) and ChapStick Moisturizer, Strawberry Flavor (CCI) will be uniquely identified by a CPT trial number. CPT will record the test material name, physical description, lot number (if available), Sponsor, and date received into the log-in database. Each of the two test materials has an expected SPF of 15.

A control standard (Reference Sunscreen Formulation) will be run concurrently with the test materials. Three control standards are delineated within the methodology as follows:

Control Standard	Mean SPF	Acceptance Limits (Mean $\pm$ 2SE)	
		Lower limit	Upper Limit
P2	16.1	13.7	18.5
P3	15.7	13.7	17.7
P7	4.4	4.0	4.8

For the two test materials in this trial, control standard P2 will be used.

## 4.2 Storage

ChapStick Moisturizer, Classic Flavor, and ChapStick Moisturizer, Strawberry Flavor, unless otherwise specified, will be stored at ambient temperature and humidity in the container(s) in which they are received by CPT.

The control standard will be stored in a refrigerator at 4°C to 8°C and ambient humidity. The control standard will be allowed to warm to room temperature prior to use (approximately 60 minutes).

## 4.3 Disposition

All remaining test materials (unused and used, including empty containers) will be returned to the Sponsor at the following address within 2 months of trial completion:

GSK Consumer Healthcare R&D  
Consumer Study Supplies  
[name]  
[name]  
Attention: Returned Study Supplies  
Protocol #215232

PPD

The control standard will be returned to the refrigerator and used in additional trials until the entire control standard has been used or the expiration date has been reached.

## 5 Selection and Withdrawal of Subjects

### 5.1 Number of Subjects

Potential subjects will be recruited for the clinical trial from the CPT database per the CPT standard operating procedure.

An initial assessment of up to 5 valid subjects may be conducted to evaluate a preliminary SPF value. An additional 5 valid subjects may be added to the initial 5 subjects to form a complete panel. Per the ISO24444 (2010) test method, testing of up to 25 subjects may be needed to achieve a minimum of 10 valid results (see below for more detail). For this trial, the maximum number of qualified subjects has been set by the Sponsor to 15 subjects. Addition of subjects beyond 15 must be approved in writing by the Sponsor. Results shall be recorded for each panel.

A maximum of 5 individual results from qualified subjects may be excluded from the calculation of the mean SPF but each exclusion must be justified (Section 7.1). A minimum of 10 valid subjects is only sufficient if the 95% confidence interval of the mean SPF is within  $\pm 17.0\%$  of the mean SPF. Otherwise, the number of subjects shall be increased stepwise from 10 until the statistical criterion is met, up to a maximum of 20 valid results from a maximum of 25 qualified subjects tested. If the statistical criterion has not been met after 20

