## 6.3 Determination of Minimal Erythmal Dose on Protected Skin (MEDp)

### 6.3.1 Test Material Application

The test sites expected to be used in this trial will be 40 cm^2. A sufficient number of 40 cm^2 test sites shall be outlined with a surgical marking pen on the subject's back between the scapulae and the beltline, lateral to the midline, while avoiding any anatomical areas containing extreme curvature. The lines shall be drawn on the subject while in the testing position (upright or prone). These test sites shall be designated for the test material(s) and control standard, with an adjacent test site designated for a concurrent MEDu determination (Section 6.2.1).

Assignment of the test sites for test material(s), control standard, and MEDu shall follow a randomization schedule generated using a validated version of the statistical software R 3.6.1. For each subject, 4 test sites will have a random assignment number for up to two test materials, control standard, and MEDu, with at least 3 of the test sites being utilized for application. If a subject is tested at only 3 test sites, the subsequent randomization assignment will also involve only 3 test sites, with the corresponding test material used as the primary assignment to maintain balancing of treatment allocation.

Test material preparation, test material application, UV exposures, and MED assessments shall each be performed by trained technicians in ambient conditions (18-26°C) according to CPT's SOPs and the International Standard Test Method (reference 12.1).

A portion of test material(s) or control standard shall be applied to the appropriate 40 cm^2 test site and spread evenly over the test site using a finger cot that has not been pre-saturated with the test material or control standard. This application shall provide a test material film of approximately 2.00 ± 0.05 mg/cm^2, using 80 ± 2 mg of material. The actual weight applied shall be recorded on the CRF. To aid spreading, droplets of test material or control shall be deposited within the test site, and then spread over the whole test site using light pressure. Spreading time should be in the range of 35 ± 15 seconds.

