## 7 Statistical Methods

### 7.1 Rejection of Data

Test data from a qualified subject shall be invalid and rejected for any of the following reasons:

- If the exposure series fails to elicit an MED response on either the treated or unprotected test sites;
- If the responses on the treated test sites are randomly absent (which indicated the test material (or control standard) was not spread evenly);
- If all subsites on the exposure series show an erythema response upon evaluation; or
- If the subject was noncompliant (e.g., subject withdraws from the test due to illness or work conflicts; subject does not shield the exposed test sites from further UV radiation until the MED is read, etc.).

If data are rejected for any one test material on more than 5 qualified subjects, then the entire test for that material is invalid and shall be rejected. If data are rejected for the control standard (Reference Sunscreen Formulation) on more than 5 qualified subjects, then the entire test is invalid and shall be rejected.

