#### CONFIDENTIAL

This document is a confidential communication of Consumer Product Testing Company, Inc. containing Testing Facility capabilities and processes, and as such, is intended solely for the use of the Sponsor and Testing Facility in the performance of services. The confidential information contained herein, shall only be released by either Party upon compelled disclosure in compliance with legal or regulatory requirement.

where c is calculated as:

$$c = (t \text{ value}) \times \text{SEM} = (t \text{ value}) \times s / \sqrt{n}$$

$$c = t \times s / \sqrt{n}$$

$$\text{CI}[\%] = 100 \times c / \text{SPF}$$

SEM = standard error of the mean

n = total number of subjects used

t = t value from the "two-sided" Student-t distribution table at a probability level  $p = 0.05$  and with degrees of freedom  $\nu = (n-1)$

The statistical criterion for all SPF measurements is that the 95% CI on the mean SPF measured shall fall within a range of  $\pm 17.0\%$  of the measured mean SPF. This applies to test material SPF measurement and control standard SPF measurement.

Consequently, the actual number of subjects tested is defined as the number (minimum ten) required to produce a mean test material (or control standard) SPF with a 95% CI, which

falls within a range of  $\pm 17.0\%$  of the measured mean SPF for the test material and a mean reference SPF which has a 95% CI that falls within the range of  $\pm 17.0\%$  of the measured mean SPF for the control standard.

A minimum of 10 valid results is only sufficient if the statistical criterion is fulfilled. If not, the number of subjects may be increased from ten until the statistical criterion is met up to a maximum of 20 valid results (i.e., a maximum of 20 valid results plus 5 rejected invalid results). **Note that for this trial the Sponsor has set a maximum of 15 subjects. Written approval is needed from Sponsor if more than 15 subjects are required.** For details on the sequential procedure and calculations, see reference 12.1.

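### Does the Sponsor's 15-subject cap clash with the plan's other counts and leave the outcome open if extension is refused?

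*Combined protocol and SAP*

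**What the plan says.** All references are to the combined protocol and SAP.

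- **5.1 Number of Subjects.** Ten valid subjects suffice only if the 95% confidence interval of the mean SPF lies within ±17.0% of that mean. At most 5 results may be excluded. If ten are not enough, "Otherwise, the number of subjects shall be increased stepwise from 10 until the statistical criterion is met", up to 20 valid results from 25 subjects; a test that still misses there is rejected. The cap is stated thus: "For this trial, the maximum number of qualified subjects has been set by the Sponsor to 15 subjects". The Sponsor must agree in writing to any more.
- **7.3 SPF Calculation for a Test Material for the Panel.** The ±17.0% criterion applies to the test materials and to control standard P2. "A minimum of 10 valid results is only sufficient if the statistical criterion is fulfilled"; failing that, "the number of subjects may be increased from ten until the statistical criterion is met". The upper limit is explained as 20 valid results plus 5 rejected ones. The cap is repeated: "Written approval is needed from Sponsor if more than 15 subjects are required".
- **7.1 Rejection of Data.** "If data are rejected for any one test material on more than 5 qualified subjects", the test of that material is invalid. The same limit for the control standard invalidates the entire test.
- **6.3.1 Test Material Application.** Four sites per subject are randomised among up to two materials, the control and MEDu, with at least three used for application. "If a subject is tested at only 3 test sites, the subsequent randomization assignment will also involve only 3 test sites". The sentence goes on to say which material leads that next assignment and gives balance between treatments as the reason.
- **7.4 and 11.8.** The listing carries a passed or failed grade. The final report gives all valid and rejected individual values, the mean and its confidence interval.

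Sections 5.1 and 7.3 refer to the ISO standard (reference 12.1) for details of the sequential procedure.

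**The concern.** Three things look wrong.

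First, the same step is mandatory in 5.1 (*shall*) and permissive in 7.3 (*may*), and the cap then makes it conditional on approval.

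Second, the cap counts subjects, while the minimum of 10 and the limit of 5 exclusions apply to each SPF measurement. The two agree only if every subject carries both materials. A subject tested at three sites has room for the control, MEDu and one material, and the balancing rule for the next subject reads that way. Fifteen subjects need not then give 10 valid results per material, and 7.1 would not reject the test, because no more than 5 results had been excluded.

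Third, the stated rejections arise at 20 valid results from 25 subjects, or above 5 exclusions. Neither covers a shortfall at 15 subjects with approval refused or not sought.

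The stake would be the status of the primary result. A measurement could end neither accepted nor rejected, and the decision could be taken after the data were seen.

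**Working it through.** **1. The plan's own counts.** 10 valid + 5 excluded = 15, the cap. 20 valid + 5 excluded = 25, the method's ceiling. Both reproduce exactly, so the cap is the smallest number of subjects that secures 10 valid results when every subject carries both materials and all 5 exclusions are used.

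**2. One-material subjects.** Let *p* be the number of balanced pairs of such subjects. Each pair costs each material one result, so results per material = 15 − *p*, and valid results after 5 exclusions = 15 − *p* − 5.

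| *p* | Results per material | Valid after 5 exclusions |
|---|---|---|
| 0 | 15 | 10 |
| 1 | 14 | 9 |
| 3 | 12 | 7 |
| 5 | 10 | 5 |
| 6 | 9 | 4 |

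The shortfall is arithmetically possible from *p* = 1. The documents do not give *p*, and it may be 0. The table also assumes that every permitted exclusion is used. If each result is valid with probability 90% (an assumption), the binomial chance of at least 10 valid is 99.8% from 15 results, 99.1% from 14, 88.9% from 12 and 34.9% from 10.

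**3. Precision at the cap.** Section 7.3 defines CI[%] = 100 × *t* × *s* / (√*n* × SPF). Setting this to 17.0, the largest passing coefficient of variation (CV) is 17.0 × √*n* / *t*:

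- *n* = 10: 17.0 × 3.162 / 2.262 = 23.8%
- *n* = 15: 17.0 × 3.873 / 2.145 = 30.7%
- *n* = 20: 17.0 × 4.472 / 2.093 = 36.3%

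The plan gives no CV for the individual SPF values, so 20%, 25% and 30% are assumed. Simulation with a look at every *n* from 10 gives the chance that one measurement has not yet met the criterion (lognormal / normal values):

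| Assumed CV | 10 valid | 12 valid | 15 valid | 20 valid |
|---|---|---|---|---|
| 20% | 17% / 19% | 5% / 5% | 0.4% / 0.4% | 0% / 0% |
| 25% | 49% / 52% | 27% / 30% | 8% / 10% | 0.6% / 0.5% |
| 30% | 74% / 76% | 56% / 60% | 32% / 36% | 8% / 9% |

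These are per measurement. There are three (two materials and P2), so the chance that at least one misses is at most three times as large: about 3 × 0.4% = 1.2% at a CV of 20% with 15 valid results.

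**4. What the text does in each case at 15 subjects.**

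| State at 15 subjects | What applies |
|---|---|
| At least 10 valid, CI[%] ≤ 17.0 | Sufficient (5.1, 7.3) |
| More than 5 results rejected | Invalid (7.1) |
| Fewer than 10 valid, or CI[%] > 17.0, approval given | Continue, up to 20 valid plus 5 rejected (5.1, 7.3) |
| The same, approval not given | No disposition stated; not sufficient under 7.3 |

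Only the last row lacks a named outcome. Even there, 7.3 requires the interval to lie within ±17.0% and defines the number tested as the number, at least ten, that achieves this for the material and for P2 together. The measurement has therefore not met the criterion. The *may* in 7.3 does not change that: stopping early with a miss is still a miss.

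**The case for a change.** The strongest case for a change is that acceptance of the primary result should not depend on inference. The two verbs do differ, the counting units do differ, and no sentence covers refusal. The cap is the Sponsor's own for this trial, so the ISO standard cannot be assumed to settle the point, and that standard was not available for this check. If the CV were 25–30%, or several subjects carried one material, the situation would not be rare. The remedy would be wording only.

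The textual observations stand. Four things limit their weight.

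- The cap is stated for the trial as a whole, so a per-material reading has little support. Section 7.3 explains the upper limit as 20 valid plus 5 rejected results, which counts results for a measurement. A clash at 25 subjects appears only if that explanation is set aside.
- Section 6.3.1 is unclear. The default is four sites, and at least three are to be used for application. MEDu receives no application, so read literally every subject carries both materials and P2, and *p* = 0. The sentence on balancing favours the other reading. One-material subjects are plausible, not established.
- A shortfall at 15 is a foreseen event with a stated route, namely written approval.
- P2 is not left open: 7.3 makes its precision a joint requirement with that of the material. A three-site subject on the one-material reading still carries P2, so P2 loses no results.

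Under 11.6 even a wording change needs a formal amendment approved by the PI, the Sponsor and the IRB.

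**Conclusion.** No change is needed. The differing verbs are a clerical inconsistency, and the unstated outcome is a gap that an analyst following 7.3 fills in one way: a measurement with fewer than 10 valid results, or CI[%] above 17.0, has not met the criterion and cannot be graded as passed. The cap is a budget gate that matches 10 + 5, with a written route past it.

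The worst-case shortfall is one valid result per pair of one-material subjects (9 instead of 10 at *p* = 1), and it needs all 5 exclusions to be used. With 15 valid results, the chance that a measurement misses precision at the cap is about 0.4% at a CV of 20%, 8–10% at 25% and 32–36% at 30%. The CV, the 90% validity rate and *p* are assumptions, because the documents give none of them.

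The conclusion does not rest on a miss being rare. It rests on a miss being a non-pass under the text as it stands, with every individual value and the interval reported. Harmonising the verb, naming the counting unit or writing down the disposition would make the plan easier to read. It would not alter an SPF value, an interval or the set of measurements that meet the criterion.
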